**Other AEs:**

The severity of all AEs other than solicited AEs and abnormal clinical safety laboratory test results reported as AEs will be assessed by the investigator and participant (as applicable) based on the Division of AIDS (DAIDS) Table for Grading the Severity of Adult and Pediatric Adverse Events, corrected version 2.1, July 2017, of the US National Institute of Health, available from:

<https://rsc.niaid.nih.gov/sites/default/files/daidsgradingcorrectedv21.pdf>

The severity grading criteria provided grade AEs from mild (grade 1) to life threatening (grade 4). All AEs leading to death are Grade 5 events. AEs are graded with the worst severity grade during the illness/symptoms. Life threatening events and events leading to death must be reported as SAEs.

#### **8.4 Causality of Adverse Event**

The study investigators will determine the causal relationship between the study vaccine and the AE. The causality assessment is made based on the available information at the time of reporting and can be subsequently changed according to follow-up information. Assessment of causality is based on clinical judgment and should take into consideration the following factors:

- Is there a temporal relationship between the event and administration of the study vaccine?
- Is there a plausible biological mechanism for the study vaccine to cause the AE?
- Is there a possible alternative etiology for the AE such as concurrent illness, concomitant medications?
- Are there previous reports of similar AEs associated with the study vaccine or other vaccines in the same class?

For this study, the investigator must classify the causality of the AE according to the categories defined below:

**Related:** There is a reasonable possibility that the study vaccine caused the event. “Reasonable possibility” means that there is evidence to suggest a causal relationship between the study vaccine and the AE.

**Not Related:** There is not a reasonable possibility that the administration of the study vaccine caused the event.

#### **8.5 Follow-up of Adverse Event**

All reported AEs should be followed until resolution or stabilization, or until the participant’s participation in the study ends. The investigator must ensure that any AEs that are ongoing at study completion have been appropriately referred to the local health care system for continuation of care. Participants who have an ongoing study vaccine related SAE at study completion or at discontinuation from the study will be followed by the investigator until the event is resolved or determined to be irreversible, chronic, or stable by the investigator.

The outcome of adverse events will be assessed at the time of last observation as per the following categories:

- Recovered/resolved without sequelae
- Recovered/resolved with sequelae
- Recovering/resolving
- Not recovered/not resolved
- Fatal
- Unknown. The outcome of the AE is not known

Due to uncertainties around the COVID-19 pandemic, if a subject has a reportable adverse event that meets the clinical criteria of the current CDC case definition of COVID-19, the investigator will ensure that the subject will undergo standard of care diagnostic testing and if needed, a quarantine period for SARS-CoV-2.

## 8.6 General Guidance on Recording Adverse Events

To improve the quality and precision of acquired AE data, the investigator should observe the following guidelines:

- AEs must be assessed for severity (graded) and causality and reviewed by the site investigator.
- If an AE (e.g., low hemoglobin) meets the criteria for two different severity grades simultaneously (e.g., Grade 1 for absolute hemoglobin level and Grade 2 for change from baseline value), the severity grade reported should be the most severe grade (i.e., Grade 2 in the example provided).
- Whenever possible, use recognized medical terms when recording AEs on the AE CRF. Do not use colloquialisms or abbreviations.
- If known, record the diagnosis (i.e., disease or syndrome) rather than component signs, symptoms and laboratory values (e.g., record congestive heart failure rather than dyspnea, rales, and cyanosis); however signs and symptoms that are considered unrelated to an encountered syndrome or disease should be recorded as individual AEs (e.g., if congestive heart failure and severe headache are observed at the same time, each event should be recorded as an individual AE).
- AEs occurring secondary to other events (e.g., sequelae) should be identified by the primary cause. A “primary” AE, if clearly identifiable, generally represents the most accurate clinical term to record. If a primary serious AE (SAE) is recorded, events occurring secondary to the primary event should be described in the narrative description of the case. For example:

Orthostatic hypotension® Fainting and fall to floor® Head trauma® Neck pain

The primary AE is orthostatic hypotension.

- Death is an outcome of an event. The event that resulted in the death should be recorded and reported on the SAE CRF.
- For hospitalizations for surgical or diagnostic procedures, the illness leading to the surgical or diagnostic procedure should be recorded as the SAE, not the procedure itself. The procedure should be captured in the case narrative as part of the action taken in response to the illness.
- Pregnancies that occur in study participants are not considered AEs and will be recorded on a separate Pregnancy CRF. Pregnancy outcomes that include spontaneous abortion, stillbirth or any congenital anomaly must be reported as SAEs.

## 8.7 Reporting of SAEs

PATH has designated Emmes with authority to coordinate SAE reporting activities. All SAEs which occur during the study, whether considered to be associated with the study vaccine or not, must be reported within 24 hours of the site becoming aware of the event to the Emmes Medical Monitor by one of the mechanisms provided (e.g., electronic data capture [EDC] system, email, or fax). Contact details and instructions for submitting SAEs will be provided in a handout located in the Investigator Site File. If the SAE is fatal or life-threatening, the study medical monitor shall be informed immediately by email.

The investigator should not wait for additional information to fully document the event before notifying Emmes. When additional information becomes available, follow-up submissions will be submitted. The initial SAE form should be completed with all information known at the time and should include minimal elements for initial assessment:

- Name and contact of the investigator submitting the SAE report
- Participant ID number
- Date participant received study vaccine

- Description of the SAE and date of event onset
- Investigator's preliminary assessment of severity and causality

When applicable, hospital case records and autopsy reports should be obtained (without name or personal identifiers).

The investigator is also responsible for reporting all SAEs to their IRB/IEC in accordance with institutional policy and adequate documentation of this reporting must be provided to Emmes.

Reporting procedures for all SAEs will be followed as per FDA regulatory guidelines. The study Safety Management Plan (SMP) will contain all the details of safety and regulatory reporting. Emmes is responsible for safety reporting to the FDA within the following time periods:

- Serious and unexpected suspected adverse reaction within 15 days of awareness
- Fatal or life-threatening suspected adverse reaction within 7 days of awareness

## **8.8 Protocol Deviations**

A protocol deviation is any noncompliance with the clinical trial protocol, GCP, or site SOP requirements. The noncompliance may be either on the part of the participant, the PI, or the study site staff. As per ICH E6(R2), the investigator must not deviate from the protocol unless it is required to eliminate an immediate hazard to a trial participant. If required, as soon as is possible, the implemented deviation and the reason for it should be submitted to the IRB/IEC and PATH and a determination made as to whether a protocol amendment is required.

Deviations can be categorized as either major or minor. Reporting requirements of deviations depend on the type or degree of deviation. The procedures for handling protocol deviations will occur as follows: The PI will be notified by study staff as soon as possible if he or she is not present when the deviation is discovered.

The timeline for reporting protocol deviations to the IRB and PATH is determined by the categorization of the deviation as major or minor. Major protocol deviations are a subset of protocol deviations that may significantly impact the completeness, accuracy, or reliability of the study data or that may significantly affect a participant's rights, safety, or well-being. For example, major protocol deviations may include failure to obtain informed consent, failure to report SAEs, enrolling participants in violation of key eligibility criteria designed to ensure a specific participant population or failing to collect data necessary to interpret primary endpoints, as this may compromise the scientific value of the trial. Major deviations that occur in this protocol will be reported to PATH in an expedited manner (within 48 hours) and to the IRB/IEC as per their stated requirements.

Minor deviations are departures from the protocol that do not involve participant safety or integrity of the study data. Minor deviations will be reported to the IRB/IEC in the context of the annual Continuing Review Report or as per their stated requirements if any different. Major deviations should also be summarized in the continuing review reports.

Knowledge of any instances of serious or continuing non-compliance with the regulations or requirements will be reported immediately to PATH and the IRB/IEC.

## 9 SAFETY OVERSIGHT

The site PIs and designated site staff will be responsible for continuous close safety monitoring of all study participants and for alerting PATH if unexpected concerns arise or once aware that any study pause criteria are met.

### 9.1 Routine Reviews by Protocol Safety Review Team (PSRT)

The Protocol Safety Review Team (PSRT), composed of the site PIs, the PATH Medical Officer and Emmes medical monitor, will routinely monitor safety throughout the duration of the trial. The PSRT will be chaired by the PATH Medical Officer and may seek additional independent expert medical opinion as dictated by needs, including referral to the IDMC, particularly for consideration of unblinded review. The Emmes statistician, with assistance of the data management staff, will prepare blinded safety reports for review by the PSRT. These reports will provide at a minimum the following information:

- accrual and participant status data regarding completion of study vaccinations and study visits
- summaries of solicited, unsolicited, and serious adverse events
- predefined abnormal safety laboratory test results
- updated medical history and concomitant medication listings

The PSRT safety review will be conducted by teleconference (or electronically when appropriate) occurring at least once monthly until all participants have completed their Day 57 study visits and as needed thereafter for the remainder of the study. In addition to safety review, the PSRT may elect to discuss trial conduct issues that impact study integrity and participant safety. These may include, but are not limited to, data quality, critical monitoring findings, study vaccine concerns, and issues with research specimens. Emmes will also notify the PSRT of the need for ad hoc safety reviews whenever it is aware of a SUSAR or adverse events that meet pre-specified study pause criteria as per section 9.3.

### 9.2 Independent Data Monitoring Committee (IDMC) Reviews

An IDMC composed of at least three independent members with expertise in vaccine clinical trials will be convened by PATH to periodically review the conduct and safety of the study. The responsibilities and procedures of the IDMC are defined in the IDMC Charter.

The IDMC will convene for an organizational meeting prior to study initiation and then for at least three scheduled meetings during the conduct of the study. For each of the two nOPV types, one meeting will be scheduled once 15 participants have completed their one week post-initial dose study vaccination visits. The third meeting will be scheduled based upon observed enrollment rates and study progress. In addition to these routinely scheduled meetings, if the PSRT has serious safety concerns or study pause criteria are met, the IDMC will convene by teleconference to jointly review the data. The IDMC reviews will be summarized with recommendations to PATH as to whether there are safety concerns and whether the study should continue without change, be modified, or be terminated.

If, at any time, a decision is made to permanently discontinue administration of study vaccines in all participants, PATH will notify the FDA and the site investigators of record will notify the responsible IRB/IEC expeditiously.

### 9.3 Study Pause Rules

The following study pause rules will automatically halt any further study vaccinations; however, participants already vaccinated will continue to be followed for safety during the pause. These pause rules

refer to suspected adverse reactions and will be triggered automatically if any of the criteria described below are met in a specific study group during the conduct of the study:

- One or more participants experience an SAE that cannot reasonably be attributed to a cause other than study vaccine
- Three or more participants experience the same severe (grade 3) solicited AE within 7 days following study vaccination that cannot reasonably be attributed to a cause other than study vaccine
- Three or more participants experience the same severe (grade 3) unsolicited AE (including laboratory abnormality) within 28 days following study vaccination that cannot reasonably be attributed to a cause other than study vaccine

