### **8.1.2 Adverse reaction / Suspected Adverse Reaction (21CFR Part 312.32)**

**Suspected adverse reaction** is any adverse event for which there is a reasonable possibility that the vaccine caused the adverse event. For the purposes of IND safety reporting, "reasonable possibility" means there is evidence to suggest a causal relationship between the vaccine and the adverse event. Suspected adverse reaction implies less certainty about causality than adverse reaction, which means any adverse event caused by a vaccine.

**Adverse reaction** is any adverse event caused by the vaccine. Adverse reactions are a subset of suspected adverse reactions for which there is reason to conclude that the vaccine caused the event.

**Unexpected adverse event or unexpected suspected adverse reaction** refers to an event or reaction that is not listed in the IB or is not listed at the specificity or severity that has been observed.

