#### **9.4 Study Pause Procedure**

The PSRT will be notified immediately by Emmes if they ascertain that a pause rule has been met. If a site investigator or the PSRT first become aware that a pause rule has been met, they will inform Emmes immediately. Emmes will cease randomization and notify the site PIs that a pause rule has been met and that no further enrollment should occur, and no study vaccines are to be administered until specific notification is provided that study vaccinations can resume.

As soon as it is confirmed that a study pause rule has been met, the IDMC will be notified and will expeditiously (within 48 hours, if possible) convene by teleconference to review all available, relevant information, including initial exclusive access to unblinded data. The IDMC reviews will be summarized with recommendations to PATH as to whether there are safety concerns and whether the study should continue without change, be modified, or be stopped.

If at any time, a decision is made to permanently discontinue administration of study vaccine in all participants, notification will be provided by PATH to the NRA and by the PI to the IRB/IEC within 48 hours.

If PATH re-starts the study after IDMC review and recommendation, enrollment and study vaccination may resume. The PIs will report the study pause and decision to resume to their IRB/IEC.

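### Section 9.3 scopes the pause rules to suspected adverse reactions, but a Related SAE that also has a reasonable alternative cause does not trigger the automatic halt

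*Protocol*

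**What the plan says.** The lead-in to protocol section 9.3 says of the criteria for a pause that they "refer to suspected adverse reactions and will be triggered automatically if any of the criteria described below are met in a specific study group". Section 8.1.2 says that a suspected adverse reaction "is any adverse event for which there is a reasonable possibility that the vaccine caused the adverse event". Section 8.4 defines Related by the same test. Both sections explain that such a possibility requires evidence pointing to a causal link.

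Under 8.4, "the investigator must classify the causality of the AE according to the categories defined below". There are two categories, Related and Not Related. One of the four factors to weigh is: "Is there a possible alternative etiology for the AE such as concurrent illness, concomitant medications".

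The first bullet of 9.3 reads "One or more participants experience an SAE that cannot reasonably be attributed to a cause other than study vaccine". The third begins "Three or more participants experience the same severe (grade 3) unsolicited AE (including laboratory abnormality) within 28 days following study vaccination" and ends with the same attribution clause. The second, on grade 3 solicited events, carries that clause too.

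A met rule stops all further vaccination (9.3). It also brings the IDMC together, within 48 hours if possible, with first and sole access to unblinded data (9.4). Site staff are responsible "for alerting PATH if unexpected concerns arise or once aware that any study pause criteria are met", and 9.4 adds: "The PSRT will be notified immediately by Emmes if they ascertain that a pause rule has been met".

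**The concern.** The lead-in and the bullets use different causality tests. The lead-in asks whether the vaccine is a reasonable possibility. The bullets ask whether anything else could reasonably explain the event. Both answers can be yes for the same event, because 8.4 makes an alternative cause only one consideration among four.

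This is a first-in-human trial, and the one-SAE rule is the only provision that stops dosing automatically after a single serious event. Outside scheduled meetings, the IDMC convenes only if a pause rule is met or the Protocol Safety Review Team (PSRT) is seriously concerned (9.2). The first scheduled meeting for each type waits until 15 participants have had their one-week visits. For a Related SAE that misses the bullet, halting and unblinded review therefore rest on the judgement of a PSRT that works from blinded reports (9.1).

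**Working it through.** **Step 1: compare the two tests.** Cross the 8.4 assessment with the attribution clause in 9.3.

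| 8.4 assessment | Another reasonable cause? | Suspected adverse reaction (8.1.2)? | Attribution clause met? |
|---|---|---|---|
| Related | No | Yes | Yes |
| Related | Yes | Yes | **No** |
| Not Related | No | No | Yes |
| Not Related | Yes | No | No |

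Row 2 is the gap. Suppose the lead-in only describes the rules: the bullet governs, and row 2 does not pause. Suppose instead that an event must satisfy both lead-in and bullet: row 2 still fails the bullet. Row 3 shows that the tests are not nested. An unexplained SAE without positive evidence against the vaccine can be Not Related and yet meet the clause.

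**Step 2: what a row 2 SAE receives.** It gets reporting within 24 hours (8.7), ad hoc PSRT review if it is a SUSAR (9.1), and an IDMC meeting if the PSRT is seriously concerned (9.2). None of these is an automatic halt. Three row 2 grade 3 unsolicited events of one kind in a study group also miss their bullet, without the SAE-specific steps.

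**Step 3: how many Related SAEs.** The protocol gives no expected rate for nOPV1 or nOPV3. Section 1.5 reports no vaccine-related SAE for the parent candidate nOPV2-c1.
- Recipients: 15 + 100 + 17 + 49 + 138 + 150 = 469.
- One-sided 95% upper bound for 0 of 469: 1 − 0.05^(1/469) = 0.637%.
- Applied to this trial: 0.00637 × 150 = 0.96 and 0.00637 × 230 = 1.46 Related SAEs.

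Only those with a reasonable alternative cause fall in row 2, and that share is unknown. The unsolicited bullet cannot be sized: 1.5.1 excludes related severe unsolicited events for children and infants only.

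**Step 4: exposure while dosing continues.** Sixteen months of recruitment (6.1) is about 487 days, or 69.6 weeks.
- All doses: 150–230 first plus 90–150 second = 240–380. Per week: 240/69.6 = 3.4 to 380/69.6 = 5.5.
- nOPV doses: 90–140 first plus 60–100 second = 150–240. Per week: 150/69.6 = 2.2 to 240/69.6 = 3.4.

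These are averages. For Cohorts 1 and 2, up to 10 participants may be vaccinated in the first week (section 3).

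**Step 5: cost of one extra pause of L days.** Doses delayed are L × 240/487 to L × 380/487. Second doses pushed past the +2-day window are (L − 2) × 90/487 to (L − 2) × 150/487.

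| L (assumed) | Doses delayed | Second doses out of window |
|---|---|---|
| 2 days | 1.0–1.6 | 0 |
| 7 days | 3.4–5.5 | 0.9–1.5 |
| 14 days | 6.9–10.9 | 2.2–3.7 |

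**The case against.** The strongest reply is that 9.3 can be read as class first and threshold second: among suspected adverse reactions, only those with no other reasonable cause stop the trial. That is a coherent choice by a sponsor, and on that reading there is no contradiction. It does not close the gap, because the row 2 event still does not pause dosing. Treating the bullets as a loose restatement of the lead-in would close most of it, but their words match neither 8.1.2 nor 8.4.

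The backstops are substantial and this part stands. Every SAE reaches the medical monitor within 24 hours. With no earlier human data on these products, most Related SAEs would probably count as unexpected, and so as SUSARs; that is an inference, since the Investigator's Brochure is not shown. The PSRT can ask the IDMC for unblinded review. An investigator who sees another cause may also record Not Related, which takes the event out of row 2.

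A reader might infer three stronger points that the documents do not support:
- *That the bullets are simply a stricter form of Related, so the clause should be replaced.* Row 3 shows otherwise. Where the bullet alone governs, replacement would drop the unexplained SAE for which evidence against the vaccine is lacking.
- *That nobody is assigned the attribution judgement.* Under 8.4 the investigators determine causality and must weigh alternative causes, and sections 9 and 9.4 set out who reports a met rule. The IDMC charter and safety management plan are not shown and may add detail.
- *That the solicited bullet needs the same change.* Under 8.1.1, causality need not be assessed for solicited events that begin in the solicitation period, so a Related category may not exist for them.

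**Conclusion.** The point holds in limited form. The scope in the 9.3 lead-in and the trigger in its first and third bullets use causality tests that overlap but differ. A Related SAE with a reasonable alternative cause falls between them: it brings no automatic halt and no expedited unblinded IDMC review. The same is true of three or more grade 3 unsolicited events of one kind.

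Few such events are expected. The upper bound is about 1.0 to 1.5 Related SAEs in the whole trial, of which only an unknown part is affected. That bound assumes that the nOPV2-c1 experience, which includes children and infants, carries over to all nOPV and mOPV arms. The dose counts assume even dosing over 16 months, all second doses given and otherwise on their due day, and illustrative pause lengths.

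This is a cheap safety improvement that should be made in a first-in-human trial. It does not show that such events would go unreviewed.

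**What to change.** In the first and third bullets of 9.3, keep the existing attribution clause and put the recorded category before it as an alternative. Bullet 1 would then cover an SAE that *is assessed as Related to study vaccine (section 8.4) or that* meets the present clause. Bullet 3 takes the same insertion after its 28-day window. Leave the solicited bullet, lead-in, counts, grades and windows unchanged.

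The SAE trigger can then be applied from the first report, because the initial SAE form already carries the investigator's preliminary causality assessment (8.7). Row 2 events now pause dosing, and no event that pauses it today is lost.

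The change is two insertions, plus matching wording in the IDMC charter and safety management plan if they repeat the rules. The downside is an occasional extra pause for an event that the IDMC then attributes to something else. The 48 hours in 9.4 is a target for convening, so a pause may last longer. At 7 to 14 days, about 1 to 4 second doses would fall outside the window. Those participants could lose Day 57 per-protocol status, but 11.4.4 sets membership by time point, so their Day 29 data need not be lost.
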